4. TREATMENTS

4.1 TREATMENTS TO BE ADMINISTERED

The study medication will be provided by BI.

4.1.1 Identity of BI investigational product and comparator products

The characteristics of the test and comparator products are as shown in Tables 4.1.1: 1, $\underline{4.1.1:}$ 2, $\underline{4.1.1:}$ 3 and $\underline{4.1.1:}$ 4.

Table 4.1.1: 1 Test product: capsaicin + diclofenac gel

Substance:	Capsaicin Diclofenac sodium
Pharmaceutical formulation:	Gel
Source:	C.P.M. ContractPharma GmbH & Co. KG Arzneimittelherstellung und Verpackung
Unit strength:	0.075% capsaicin 2% diclofenac sodium 50g tubes
Posology	The single dose of the combination product (diclofenac sodium 2% and capsaicin 0.075%) is 2 g formulation (40 mg diclofenac sodium, 1.5 mg capsaicin) to be applied on the skin. A twice daily application is proposed resulting in maximum daily dose of 4 g formulation (80 mg diclofenac sodium, 3.0 mg capsaicin).
Route of administration:	Topical

c03317678-02 Trial Protocol Page 25 of 69

Proprietary confidential information © 2016 Boehringer Ingelheim International GmbH or one or more of its affiliated companies

Table 4.1.1: 2 Comparator product 1: diclofenac gel

Substance:	Diclofenac sodium
Pharmaceutical formulation:	Gel
Source:	C.P.M. ContractPharma GmbH & Co. KG Arzneimittelherstellung und Verpackung
Unit strength:	2% diclofenac sodium 50g tube
Posology	The single dose of the diclofenac gel (diclofenac sodium 2%) is 2 g formulation (40 mg diclofenac sodium) to be applied on the skin. A twice daily application is proposed resulting in maximum daily dose of 4 g formulation (80 mg diclofenac sodium).
Route of administration:	Topical

Table 4.1.1: 3 Comparator product 2: capsaicin gel

Substance:	Capsaicin
Pharmaceutical formulation:	Gel
Source:	C.P.M. ContractPharma GmbH & Co. KG Arzneimittelherstellung und Verpackung
Unit strength:	0.075% capsaicin 50g tube
Posology	The single dose of the capsaicin gel (capsaicin 0.075%) is 2 g formulation (1.5 mg capsaicin) to be applied on the skin. A twice daily application is proposed resulting in maximum daily dose of 4 g formulation (3.0 mg capsaicin).
Route of administration:	Topical

c03317678-02 Trial Protocol Page 26 of 69

Proprietary confidential information © 2016 Boehringer Ingelheim International GmbH or one or more of its affiliated companies

Table 4.1.1: 4 Comparator product 3: placebo gel

Substance:	N/A
Pharmaceutical formulation:	Gel
Source:	C.P.M. ContractPharma GmbH & Co. KG Arzneimittelherstellung und Verpackung
Unit strength:	Not applicable
Posology	The single dose of the placebo gel is 2 g formulation to be applied on the skin. A twice daily application is proposed resulting in maximum daily dose of 4 g formulation.
Route of administration:	Topical

4.1.2 Method of assigning patients to treatment groups

When a patient is qualified for randomisation, treatment assignment will be by means of a third-party randomisation system at Visit 1. This will involve the use of IRT, which will take into consideration the relevant stratification factors (for further details see Section 7.6). To facilitate the use of IRT, the Investigator will receive all necessary instructions and/or documents for using the IRT.

Patients will be randomly assigned, in a 3:3:3:1 ratio, to either:

- (i) diclofenac and capsaicin
- (ii) diclofenac
- (iii) capsaicin
- (iv) placebo

For further details refer to Section 7.6. Entry into the application site stratum "back pain" will be capped as soon as 60% of the total trial population have been allocated to this stratum. Vice versa, the application site stratum "neck pain" will be capped as soon as 60% of the total trial population have been allocated to this stratum.

Patient assignment to the treatment groups will be determined by a computer generated random sequence. Access to the randomisation code will be controlled and documented. For further details please refer to Sections 4.1.5.1 and 4.1.5.2.

A single trial medication kit corresponding to the assigned medication number should be given to the patient and the number of the kit that was/were dispensed will be entered in the eCRF. Using this procedure, relevant parties will be blinded to the treatment group assignment.

Proprietary confidential information © 2016 Boehringer Ingelheim International GmbH or one or more of its affiliated companies

4.1.3 Selection of doses in the trial

Both, capsaicin and diclofenac are contained as single active compounds in marketed products. The doses of the active ingredients in this trial correspond to standard doses of such products. For reference see e.g. the Summaries of Product Characteristics (SmPCs) of ABC Lokale Schmerz-Therapie Wärme-Creme 750 μ g/g and Voltarol[®] 12 Hour Emulgel[®].

4.1.4 Drug assignment and administration of doses for each patient

Patients should be equipped with disposable gloves and instructed to wear them whenever applying the trial medication.

The gel will be applied to the region on the patient's back or neck where he/she feels the pain. If possible, the application should always be done by the patient himself/herself. An area of approximately 20 cm x 20 cm (corresponding to approximately two hand sizes) will be treated, covering the region on the patient's back or neck where he/she feels the most pronounced pain as identified by POM assessment (Section 5.2). A gel drop of approximately the size of a hazelnut will applied to the patient's gloved hand and quickly massaged into the POM_{WP} area. Following applications should be administered approximately 12 hours (±4 hours) from each other but not more and not less than twice daily up until the evening before Visit 6. The minimum treatment duration is 4 days, the maximum is 7 days.

If an application of the trial medication is missed, that application should be skipped and the next application should be taken as scheduled.

Patients should be instructed not to apply their trial medication in the morning before Visits 2 and in the evening before Visit 3 as the medication will be applied at the site. They should also be instructed that the medication is to be applied lastly in the evening before Visit 6. The actual date and time of administration of the medication at the trial visit will be recorded in the eCRF.

4.1.5 Blinding and procedures for unblinding

4.1.5.1 Blinding

Patients, Investigators and everyone involved in trial conduct or analysis or with any other interest in this double-blind trial will remain blinded with regard to the randomized treatment assignments until after database lock. The randomization code will be kept secret by Clinical Trial Support up to database lock.

The incidence of unblinding due to a warming effect of nonivamide can be considered very low, since a previous study investigating nonivamide [U13-2315-01] revealed a marked proportion of patients, who perceived some warming although not treated with nonivamide, and as well, revealed a marked proportion of patients, who perceived no warming although treated with nonivamide. Blinding will further be supported by applying the study medication with gloves.

Proprietary confidential information © 2016 Boehringer Ingelheim International GmbH or one or more of its affiliated companies

4.1.5.2 Unblinding and breaking the code

Emergency unblinding will be available to the Investigator / pharmacist / investigational drug storage manager via IRT. It must only be used in an emergency situation when the identity of the trial drug must be known to the Investigator in order to provide appropriate medical treatment or otherwise assure safety of trial participants. The reason for unblinding must be documented in the source documents and/or appropriate Case Report Form (CRF) page along with the date and the initials of the person who broke the code.

4.1.6 Packaging, labelling, and re-supply

The investigational products will be provided by BI or a designated CRO. They will be packaged and labelled in accordance with the principles of Good Manufacturing Practice (GMP). Re-supply to the sites will be managed via an IRT system, which will also monitor expiry dates of supplies available at the sites.

Each medication kit will consist of one tube of 50 g gel in an outer carton. For details of packaging and the description of the label, refer to the ISF.

4.1.7 Storage conditions

The trial medication must be kept in its tightly closed original packaging under the recommended storage conditions indicated on the label. A temperature log must be maintained by the Investigator/Pharmacist/investigational drug storage manager to make certain that the medication is stored at the correct temperature. If storage conditions are found to be outside the specified range, the process outlined in the ISF should be followed.

Trial medication must be stored securely at the study sites, out of reach of children and be protected from moisture and direct sunlight, e.g. in a locked cupboard or at a Pharmacy. It may only be dispensed to trial patients fulfilling the inclusion and exclusion criteria by authorised study personnel as documented in the ISF. Receipt, usage and return of the trial medication must also be documented on the respective forms in the ISF.

All unused medication including all packaging, empty or filled, must be either returned to the Sponsor, or, following written authorisation from the Sponsor, may be destroyed at site. Receipt, usage and return must be documented on the respective forms. Account must be given for any discrepancies.

4.1.8 Drug accountability

The Investigator/ pharmacist/ investigational drug storage manager will receive the investigational drugs delivered by the Sponsor when the following requirements are fulfilled:

- Approval of the trial protocol by the Institutional Review Board (IRB) / Independent IEC Committee (IEC),
- Availability of a signed and dated clinical trial contract between the Sponsor and the head of the investigational site,
- Approval/notification of the regulatory authority, e.g. competent authority (CA),

c03317678-02 Trial Protocol

Page 29 of 69

Proprietary confidential information © 2016 Boehringer Ingelheim International GmbH or one or more of its affiliated companies

- Availability of the curriculum vitae of the principal Investigator,
- Availability of a signed and dated clinical trial protocol
- Availability of the proof of a medical license for the principal Investigator (if applicable)

The Investigator/ pharmacist/ investigational drug storage manager must maintain records of the product's delivery to the trial site, the inventory at the site, the use by each patient, and the return to the Sponsor or alternative disposal of unused products.

These records will include dates, quantities, batch / serial numbers, expiry ('use-by') dates, and the unique code numbers assigned to the investigational product and trial patients. The Investigator / pharmacist / investigational drug storage manager will maintain records that document adequately that the patients were provided the doses specified by the CTP and reconcile all investigational products received from the Sponsor. At the time of return to the Sponsor or appointed Clinical Research Organisation (CRO), the Investigator/pharmacist/ investigational drug storage manager must verify that all unused or partially used drug supplies have been returned by the clinical trial patient and that no remaining supplies are in the Investigator's possession.

4.1.8.1 Patient treatment compliance

Records will be kept regarding when and how much of each study medication is dispensed to, and used by each individual patient in the study. This will be done by measuring the weight of the medication tubes (with cap, without the outer packaging) prior to dispense at Visit 1 and upon return by the patient at Visit 6. Both values will be recorded in the CRF. Appropriate scales should be used which display the tube weight with at least 1 decimal place (0.1 g). Tube weights should always be determined with the same device.

CONCOMITANT THERAPY, RESTRICTIONS, AND RESCUE 4.2 TREATMENT

Rescue medication, emergency procedures, and additional treatment(s) 4.2.1

Paracetamol tablets (500 mg tablets) will serve as rescue medication as it is recommended as first line treatment in guidelines for the treatment of acute back or neck pain, e.g. the German National care guideline: low back pain [P11-08387]. Following the first application of study medication, patients may use paracetamol (one to two tablets of 500 mg per os (p.o.), up to twice daily; i.e. up to 4 tablets/ 2 g per day at maximum) for treating intolerable back or neck pain. Similar rescue concept were used in comparable clinical trials [R14-1467, R15-2151, R12-4428, R15-2150].

The patient must always record the number of tablets and the day and time a dose is taken in his/her diary.

Trial Protocol

c03317678-02 Page 30 of 69

Proprietary confidential information © 2016 Boehringer Ingelheim International GmbH or one or more of its affiliated companies

Patients should be strongly encouraged not to take any rescue medication until Visit 3. Patients are advised to seek medical advice if the pain persists or the patient's condition worsens, and/or if the rescue medication is used up.

There are no special emergency procedures to be followed.

4.2.2 Restrictions

4.2.2.1 Restrictions regarding concomitant treatment

The following concomitant treatments are not permitted during the trial for the trial indication or other indications as they would interfere with the efficacy assessments in this trial: any anti-inflammatory drugs, heparinoids, muscle relaxants or analgesics (including but not limited to long- and short-acting glucocorticoids, non-steroidal anti-inflammatory drugs [NSAIDs], herbal preparations), spinal injections, muscle relaxants, other topical pharmaceutical products at the back or neck area, antidepressants, antipsychotics, and other treatments for back or neck pain, such as physiotherapy, heat treatment (e.g. heat patch, hot water bottle), or massage, acupuncture, transcutaneous electrical nerve stimulation (TENS).

Exceptions are paracetamol as rescue medication, ASS up to 100 mg/day for cardiovascular therapy, antidepressants or antipsychotics on stable dose as from at least 2 weeks before randomisation are permitted.

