- 5. Prior use within the last 3 days before Visit 1 or concomitant use of any antiinflammatory drugs, heparinoids, muscle relaxants or analgesics (including but not limited to short-acting glucocorticoids, non-steroidal anti-inflammatory drugs [NSAIDs], herbal preparations).

Long-acting glucocorticoids must have been discontinued 10 days before study entry.

Spinal injections should have been discontinued in due time (investigator's judgement) before patient enrolment to allow complete wash-out of the active ingredient based on investigator's judgment.

Exceptions: Acetyl salicylic acid (ASS) up to 100 mg/day for cardiovascular therapy, antidepressants or antipsychotics on stable dose for at least 2 weeks prior to Visit 1. Use of inhaled glucocorticoids (e.g. for asthma or chronic obstructive pulmonary disease) is acceptable.

- 6. Non-pharmacological treatment (physiotherapy, heat treatment (e.g. heat patch, hot water bottle), or massage, acupuncture, transcutaneous electrical nerve stimulation [TENS]) or locally applied pharmacological product to the back or neck area 24 hours prior study entry and during the study period.
- 7. Known severe hepatocellular insufficiency, severe renal insufficiency or Gilbert's syndrome (Morbus Meulengracht)
- 8. Any other medical condition that would interfere with efficacy and safety assessments based on investigator's judgement or any on-going clinical condition that would jeopardize patient's or site personnel's safety or study compliance based on investigator judgement.

Proprietary confidential information © 2016 Boehringer Ingelheim International GmbH or one or more of its affiliated companies

- 9. Known intolerance or hypersensitivity to the active ingredients or any excipient(s).
- 10. Patients in whom attacks of asthma, bronchospasm, rhinitis or urticaria were precipitated by the intake of ASS or other NSAIDs
- 11. Irritated skin (based on investigator's judgement), skin wounds, eczema or open injuries at application site (the trial medication should only be applied to intact, non-diseased skin)
- 12. Negative experience in the past with heat treatments for muscle complaints (e.g. heat pads, hyperaemisations inducing topical creams, gels, ointments, patches)
- 13. Patient not able to understand and comply with trial requirements based on investigators judgement
- 14. Alcohol or drug abuse within 3 months prior to Visit 1 that would interfere with trial participation based on investigator's opinion.

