3.3.4 Removal of patients from therapy or assessments

3.3.4.1 Removal of individual patients

An individual patient is to be withdrawn from trial treatment if:

- The patient withdraws consent for study treatment or study participation, without the need to justify the decision.
- The patient needs to take concomitant drugs that interfere with the investigational product (see Section 3.3.3) or other trial medication. See Section 4.2.2 for further details.
- The patient can no longer be treated with trial medication or rescue medication for other medical reasons (such as surgery, adverse events, other diseases, or pregnancy)

If a patient becomes pregnant during the trial the study medication will be stopped, the patient will be discontinued from the trial and the patient will be followed up until birth or otherwise termination of the pregnancy.

Trial Protocol

c03317678-02 Page 23 of 69

Proprietary confidential information © 2016 Boehringer Ingelheim International GmbH or one or more of its affiliated companies

A patient can be discontinued after discussion between Sponsor and Investigator if eligibility criteria are being violated, or if the patient fails to comply with the protocol (e.g. nonattendance at study assessments).

Patients who drop out during the screening prior to randomisation will be considered screening failures. They will be recorded as screening failures in the eCRF and no further follow-up is required. The data will be included in the trial database and will be reported.

Patients who discontinue or withdraw from the study after randomisation will be considered as "early discontinuations" and the reason for this premature discontinuation must be recorded in the eCRF. The Investigator must inform the sponsor within 24 hours via IRT (see Section 4.1) about any premature discontinuation of a subject. The data will be included in the trial database and will be reported. Given the patient's agreement, the patient will undergo the procedures for early treatment discontinuation and follow up (Visits 6 and 7T) as outlined in the Flow Chart and Section 6.2.3.

For all patients the reason for withdrawal (e.g. adverse events) must be recorded in the eCRF. These data will be included in the trial database and reported.

Discontinuation of the trial by the sponsor 3.3.4.2

Boehringer Ingelheim reserves the right to discontinue the trial overall or at a particular trial site at any time for the following reasons:

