7.3 PLANNED ANALYSES

Three analysis datasets will be defined for the purpose of summarizing and analysing the trial data.

Treated set (TS): All randomised patients who used at least one dose of study medication will be included in the treated set. Patients having received the wrong treatment will be analysed within the planned (randomised) treatment group in the efficacy analysis and within the actual treatment group in the safety analysis.

Full analysis set (FAS): All patients included in the treated set, which provide a baseline value before application for POM_{WP} at Visit 1 and at least one POM_{WP} value during the assessment times Visit 1 (Day 1 morning, 1 hour after application), Visit 2 (Day 2, morning, 1 hour after application), Visit 3 (Day 2 evening, before application), Visit 3 (Day 2 evening, 1 hour after application), will constitute the full analysis set.

Proprietary confidential information © 2016 Boehringer Ingelheim International GmbH or one or more of its affiliated companies

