About 800 patients will be randomised to ensure that 700 patients are evaluable for the primary endpoint; as soon as 700 patients in total are evaluable for the primary analysis, the randomisation will be stopped. To ensure that each application site stratum "back pain" or "neck pain" is represented by at least 40% of the randomised patients, randomisation into a respective stratum will be capped as soon as 60% of the total trial population have been allocated to the respective stratum.

Calculations were performed using nQuery Advisor® 6.1 statistical package by Statistical Solutions Ltd.

Proprietary confidential information © 2016 Boehringer Ingelheim International GmbH or one or more of its affiliated companies

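### The on-study medication rules in Protocol 4.2.2.1 omit the inhaled-glucocorticoid exception that exclusion criterion 5 grants, so the protocol gives two answers for the same eligible patient

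*Protocol*

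**What the plan says.** Three places in the protocol bear on the point.

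- **Section 3.3.3, exclusion criterion 5.** The criterion opens with "Prior use within the last 3 days before Visit 1 or concomitant use" and goes on to cover anti-inflammatory drugs, naming short-acting glucocorticoids among them. It makes exceptions for low-dose aspirin in cardiovascular therapy and for antidepressants or antipsychotics on a stable dose, and adds: "Use of inhaled glucocorticoids (e.g. for asthma or chronic obstructive pulmonary disease) is acceptable".
- **Section 4.2.2.1, concomitant treatment.** The listed treatments are "not permitted during the trial for the trial indication or other indications". The list begins with "any anti-inflammatory drugs, heparinoids, muscle relaxants or analgesics (including but not limited to long- and short-acting glucocorticoids". The exceptions are given as "Exceptions are paracetamol as rescue medication, ASS up to 100 mg/day for cardiovascular therapy, antidepressants or antipsychotics on stable dose".
- **Section 3.3.4.1, withdrawal from trial treatment.** One ground is "The patient needs to take concomitant drugs that interfere with the investigational product". The sentence refers the reader to 3.3.3, extends to other trial medication, and then points to 4.2.2 for details.

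**The concern.** A patient using an inhaled steroid for asthma meets the entry criteria and, by criterion 5, may keep using it. Under the wording of 4.2.2.1 the same patient is taking a prohibited drug. No available text says which rule governs.

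The protocol foresees such patients. Criterion 5 names the two respiratory diseases, and exclusion criterion 10 removes only patients whose asthma or similar attacks were brought on by aspirin or another NSAID. The Flow Chart has concomitant therapy reviewed at every visit, so sites will meet the question.

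About 20 centres in two countries could resolve it differently. One might let the inhaler continue, another might advise stopping it, a third might record a violation, and a fourth might end trial treatment. Interrupting maintenance respiratory therapy for a 4-to-7-day trial of a topical gel would be an avoidable risk to the patient.

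**Working it through.** No formula applies; the check is a comparison of texts.

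**Step 1: do both rules cover the same period?** Yes. Criterion 5 addresses concomitant use as well as the three days before Visit 1. Section 4.2.2.1 addresses the trial period. They overlap throughout treatment, so the difference cannot be explained as an entry rule set against an on-study rule.

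**Step 2: do both cover the same drug?** Yes, on the wording. The ban in 4.2.2.1 takes in any anti-inflammatory drug, names glucocorticoids by duration of action and not by route, and extends to other indications. The same sentence does limit by location where that is meant, since other topical products are banned only at the back or neck.

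**Step 3: compare the exceptions.**

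| Exception | Criterion 5 (3.3.3) | Section 4.2.2.1 |
|---|---|---|
| Aspirin up to 100 mg/day | yes | yes |
| Antidepressants or antipsychotics, stable dose | yes | yes |
| Inhaled glucocorticoids | yes | **no** |
| Paracetamol as rescue | not listed | yes |

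Criterion 5 has 3 exceptions, 4.2.2.1 repeats 2, and 3 − 2 = 1 is missing. Section 4.2.2.1 does not refer back to criterion 5. It restates its own list, which a site can fairly take as complete.

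**Step 4: does the withdrawal rule settle it?** No. Section 3.3.4.1 cites 3.3.3, which accepts the drug, and then 4.2.2, which bans it. The rule turns on interference with the investigational product or other trial medication, whereas 4.2.2.1 justifies its ban by interference with the efficacy assessments. Withdrawal is a possible reading, not a required one.

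**Step 5: does it reach the primary analysis?** The full analysis set in Protocol 7.3 is "All patients included in the treated set, which provide a baseline value before application", together with at least one post-dose value of the primary pain measure up to Visit 3. It has no condition on medication, so a patient who is only flagged stays in. Under Protocol 7.7 randomisation stops "as soon as 700 patients in total are evaluable for the primary analysis". No effect on sample size or power can be derived from this inconsistency.

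**The case against.** The best reply is that a sensible reader applies the specific permission over the general ban. Criterion 5 contains the only statement about the inhaled route, it covers concomitant use, and it shows that the sponsor did not regard inhaled steroids as disturbing the efficacy assessments. In the withdrawal rule, the reference attached directly to interference is 3.3.3, which accepts the drug. No text tells a site to stop an inhaler. Inhaler use would also be visible in the report, because concomitant therapies are recorded and the SAP (7.2) summarises them by treatment group.

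Much of this stands. The reading is probably what the sponsor intended, and the site actions described are possibilities, not instructions. The available SAP text also lacks the content of its table of important protocol violations (Table 6.2: 1), so whether an inhaler would be flagged there is unknown; that gap is not held against the plan.

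It does not remove the conflict. The specific-over-general rule is not written down, and 4.2.2.1 repeats two exceptions from criterion 5 while omitting the third. A site or monitor who follows 4.2.2.1 as written would be acting on the protocol's own words.

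**Conclusion.** The concern holds. Two operative conduct rules contradict each other on the same drug in the same period, through one missing item out of three. It is a minor point. The consequence is uneven site handling and a literal ban on maintenance respiratory therapy for patients the protocol chose to admit. The primary analysis set, error rate and power are untouched.

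The number of patients affected cannot be stated, since neither document gives a figure for inhaled glucocorticoid use. The conclusion rests on the current protocol text and on no clarification existing in the parts that are not public. The legible part of the amendment log shows no change to either rule.

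**What to change.** Add inhaled glucocorticoids to the exceptions in Protocol 4.2.2.1, with the same two disease examples that criterion 5 uses. The two sections cited by 3.3.4.1 would then give the same answer.

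Deleting the exception from criterion 5 would also restore consistency, but it would exclude patients whom the protocol now accepts, and nothing in the documents suggests that this is wanted.

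The cost is one ten-word phrase in the next amendment. Procedures, data collection and analysis do not change.
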